9.1.2. Final analysis

A final analysis will be generated after study end and a final study report will be written.

9.2. Statistical considerations for interim analyses

Since there is no hypothesis testing, no adjustment of type I error will be needed.

10. CHANGES FROM PLANNED ANALYSES

The study cohorts and incidence rates were clarified.

11. LIST OF FINAL REPORT TABLES, LISTINGS AND FIGURES

Refer to the document entitled EPI-FLU-055 VS UK (207781) TFL.

12. ANNEX 1 STATISTICAL METHODS AND DATA DERIVATION RULES

12.1. Statistical Method

The recruitment will be performed by the GP practices and this may create a clustering effect.

Subjects medically followed by the same GP practices are more prone to receive similar treatment for a given condition than those being treated for the same condition by different physicians. Furthermore, subjects attending a single GP practice are likely to share similarities including geography, socioeconomic status, ethnic background, or age by virtue of the area in which they have all chosen to live. In the same way, GP practices which have chosen to work together are likely to share similarities.

Similarities (or homogeneity) between subjects in clusters reduce the variability of their responses, compared with that expected from a random sample. Not accounting for cluster effect would overestimate the precision of the estimated rates.

The two-sided 95% CI for a proportion within a group accounting for clustering effect will be estimated using the Clopper-Pearson exact CI modified for cluster data [Korn, E.L. and Graubard, B.I. (1998). Confidence Intervals for Proportions with Very Small Expected Number of Positive Counts Estimated from Survey Data. *Survey Methodology*, 24, 193–201].

The design effect (DE), assessing the impact of clustered data on the variance, will be estimated as follows (PROC SURVEYFREQ in SAS with CLUSTER statement):

DE = actual variance (estimated using Taylor series linearization method) over the variance of a simple random sample with the same number of observations

The intra-cluster correlation (ICC) will be estimated as follows:

$$ICC = (DE-1) / (m-1)$$

Where DE is the design effect and m is the average number of subjects per cluster

The exact two-sided 95% CI for a proportion within a group not accounting for clustering effect will be calculated using the method described in Clopper-Pearson exact CI [Clopper CJ, Pearson ES. The use of confidence or fiducial limits illustrated in the case of binomial. *Biometrika*. 1934;26:404-413].

12.2. Data derivation

12.2.1. Date derivation

The date of birth will be modified during the extract from EHR to protect personally identifiable information. The modified date of birth will contain the exact month and year of birth of the subjects, but the exact day of birth will not be provided and will be set to '01' for all the subject's birth dates.

If the vaccine administration date is incomplete or missing the following rule will be applied:

- Day missing: 15 is used (standard GSK imputation)
- Month or year is missing: vaccination not included in the statistical analysis

If the start date of the AEI is incomplete or missing, a conservative approach (worst case scenario) will be used for imputation for the vaccinated subjects. The rules for imputation are detailed below, the examples are given assuming 16OCT2017 as date of vaccine administration.

- Day missing:
 - Month of onset = month of administration: day of administration will be used (e.g. OCT2017 → 16OCT2017)
 - Month of onset > month of administration: first day of the month will be used (e.g. NOV2017 → 01NOV2017)
 - Month of onset < month of administration: AEI not included in the statistical analysis
- Month or year missing: AEI not included in the statistical analysis

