Appendix 3 ADR formVersion 1 – May 15th, 2017

CONFIDENTIAL Card unique number: 0000 0000 0000 0

Enhanced safety surveillance of seasonal influenza (flu) vaccine

Study of possible adverse events following immunisation – this surveillance is designed to capture all adverse events following immunisation. Please report if you get any symptoms following your “flu jab” (influenza vaccination).

1. About you – this information is kept confidential and won't leave your practice

About you* we need contact details, please supply a full address so we can link this to your medical record:

First name _____ Surname _____
 Address _____
 Postcode _____ Telephone: _____ Email _____ @ _____
 Signed _____ Date _____ / _____ /2017

*This personal information is only being collected to link any side effects to your record

2. When you were vaccinated / When was the influenza vaccination given

What date were you vaccinated / was the vaccine given _____ / _____ /2017

Where were you vaccinated: At your GP surgery: Yes No If no, say where: _____

3. If you were not the person vaccinated

Information about the person* Male Female Date of Birth _____ / _____ / _____

First name _____ Surname _____

4. Please report any side-effects/conditions in the 7 days after your flu vaccine

Please look at the list of possible vaccine side-effects on the next page – if the person vaccinated has experienced any adverse events – please tick the relevant box and indicate the severity

Please also mark if the symptoms/possible side effects are still persisting

Please return the card in the envelope provided to your GP – please return by post or in person.

Thank you for your help

5. If you had no side effects in the 7 days after vaccination tick and return

I/the person vaccinated has NOT had any side effects or other symptoms following vaccination:

Please return the card in the envelope provided to your GP – please return by post or in person.

Thank you for your help

Formal study name:

Post-authorisation passive enhanced safety surveillance of seasonal influenza vaccines:

Pilot study in England

GSK study abbreviation:

EPI-FLU 046 VS UK

Collaborating Study Sponsors:

University of Surrey, Guildford UK

GlaxoSmithKline Biologicals

Contact:

[name]

Professor of Primary Care and Clinical Informatics

E-mail: PPD

Telephone: +PPD

PPD

Practice Liaison Officer

E-mail: PPD

Telephone: +PPD

Enhanced safety surveillance of seasonal influenza vaccine

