6.3. Weekly vaccinated cohorts

The Weekly vaccinated cohorts (for each ISO Week 35 to 48) will include all subjects from the Total eligible registered population

- who are vaccinated with a seasonal influenza vaccine during the week of interest
- who are registered in EHR during the safety follow-up period (from vaccination up to 7 days post vaccination)

Refer to [Annex 4](#) for details of the ISO weeks.

For example, the Weekly vaccinated cohort Week 40 will include all subjects from the Total eligible registered population:

- who are vaccinated with a seasonal influenza vaccine during Week 40
- who are registered in EHR during the safety follow-up period (from vaccination up to 7 days post vaccination)

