7.3.2. Analyses of primary objectives

The weekly incidence rate (per 100 subjects) of any AEIs within 7 days* post-vaccination period reported via ADR card will be estimated by Vaccine group as follows in the Weekly vaccinated cohorts restricted to subjects who received the ADR card:

- The denominator will be the number of subjects in the Weekly vaccinated cohort for the week of interest who received the ADR card
- The numerator will be the number of subjects from the denominator who reported any AEIs on the ADR card within 7 days following vaccination with the seasonal influenza vaccine

**Day of vaccination plus the following 7 days*

The cumulative incidence rate (per 100 subjects) of any AEIs within 7 days post-vaccination period reported via ADR card will be estimated by Vaccine group as follows in the Cumulative vaccinated cohorts restricted to subjects who received the ADR card:

- The denominator will be the number of subjects in the Cumulative vaccinated cohort up to the week of interest who received the ADR card
- The numerator will be the number of subjects from the denominator who reported any AEIs on the ADR card within 7 days following vaccination with the seasonal influenza vaccine

Similarly, weekly and cumulative incidence rates will be estimated for the following AEIs within 7 days post-vaccination period reported via ADR card:

- Fever/pyrexia
- Fever $>38.5^{\circ}\text{C}$ and $>39.5^{\circ}\text{C}$ (with a temperature measurement recorded in EHR; independent of route of measurement)
- Local symptoms (i.e. local erythema)
- Any and each general non-specific symptom: drowsiness, fatigue, headache, irritability and malaise
- Any and each respiratory AE: conjunctivitis, coryza, cough, epistaxis, hoarseness, nasal congestion, oropharyngeal pain, rhinorrhoea, wheezing
- Any and each gastrointestinal AE: decreased appetite, diarrhea, nausea, vomiting
- Any and each sensitivity/anaphylaxis AE: anaphylactic reactions, facial oedema, hypersensitivity reactions
- Rash
- Any and each musculoskeletal AE: arthropathy, muscle aches / myalgia
- Any and each neurological AE: Bell's palsy, Guillain-Barre syndrome, peripheral tremor, seizure / febrile convulsions

Similarly, weekly and cumulative incidence rates of any SAEs within 7 days post-vaccination period reported via ADR card will also be generated.

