7.3.4. Analyses of tertiary objectives

The analysis on vaccine uptake is described in Section [7.2](#).

Completeness of seasonal influenza vaccination data in the EHR will be assessed by computing the percentage of subjects from the Cumulative vaccinated cohort Weeks 35-48 with data on influenza vaccines recorded in EHR, by Vaccine group:

- The denominator will be the number of subjects in the Cumulative vaccinated cohort Weeks 35-48
- The numerator will include all subjects from the denominator with the following respective data recorded in EHR:
 - Complete date of vaccination
 - Vaccine batch number
 - Both complete date of vaccination and vaccine batch number

Timeliness of vaccination data in the EHR will be assessed as follows:

- Time interval in days between the seasonal influenza vaccination dates and the dates at which the records were encoded in EHR will be summarized by Vaccine group using descriptive statistics (mean, standard deviation, median, range, first and third quartile) for the Cumulative vaccinated cohort Weeks 35-48. This time interval in days will also be graphically displayed.

Compliance in returning ADR cards is described in Section [7.3.1](#).

Timeliness of AEI reporting in EHR will be assessed as follows:

- Time interval in days between the first onset date of AEIs within the 7 days post-vaccination period and the dates at which the records were encoded in EHR will be summarized by Vaccine group and ADR cards returned status using descriptive statistics (mean, standard deviation, median, range, first and third quartile) for the Cumulative vaccinated cohort of Weeks 35-48. This time interval in days will also be graphically displayed.

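### SAP 12.2.1 sets a missing vaccination day to the 15th and keeps the subject in the 7-day incidence rates, although a month-only date cannot place the day 0-7 window or the ISO week

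*SAP*

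**What the plan says.** SAP 12.2.1 has two rules for an incomplete vaccination date. For the day: "Day missing: 15 is used (standard GSK imputation". For the rest: "Month or year is missing: vaccination not included in the statistical analysis". Only the second removes anyone.

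The Weekly vaccinated cohorts (SAP 6.3) take subjects "who are vaccinated with a seasonal influenza vaccine during the week of interest", and the Cumulative cohorts (6.4) are built in the same way. Neither requires a complete date. The primary weekly rate uses them directly: "The denominator will be the number of subjects in the Weekly vaccinated cohort for the week of interest who received the ADR card". The risk window is "Day of vaccination plus the following 7 days" (7.3.2), which is eight calendar days.

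SAP 7.3.4 indicates that day-missing subjects remain in the cohort. It counts "Complete date of vaccination" as a completeness item, and for that table "The denominator will be the number of subjects in the Cumulative vaccinated cohort Weeks 35-48". If incomplete dates had been removed from the cohort, the item would be 100% by construction.

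SAP 12.2.4 treats a subject with no reported event as not having had one. For AEI onset dates, 12.2.1 uses separate, worst-case rules: a missing onset day in the month of vaccination becomes the day of administration, and in a later month it becomes the 1st. The sensitivity analyses in 7.3.6 do not set aside imputed vaccination dates.

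**The concern.** Both the endpoint and the cohort need the day of vaccination: the endpoint for an eight-day window, the cohort for an ISO week. A date known only to the month supplies neither, yet the rule proceeds as if it did.

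Take a subject vaccinated on 3 October, day not recorded, with fever dated 4 October. The imputed window is 15-22 October, so the fever appears to precede vaccination. A subject vaccinated on 25 October with a local reaction on 26 October falls after the window. If the date check is applied, neither event counts, and both subjects remain in the denominator as event-free.

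The study exists to detect a rise in AEI frequency quickly, so a default that tends to lose vaccine-related events works in the unhelpful direction. It also places all day-missing subjects in three ISO weeks, in a study whose primary objective includes weekly rates. The timeliness summary in 7.3.4 suffers too: a vaccination on 3 October entered that day would show a lag of 3 - 15 = -12 days.

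**Working it through.** The documents give no figure for this rule, so there is none to reproduce.

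**Inputs**
- Imputed day 15 (SAP 12.2.1); window day 0 to 7 (SAP 7.3.2). The imputed window is therefore days 15-22.
- Vaccination months September (30 days), October (31) and November (30), from the vaccination period in SAP 3.1.
- ISO weeks from SAP Annex 4.
- Assumed: true vaccination day v uniform over the month. The share p of day-missing records is not in the documents; a range is shown.

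**Share of dated AEIs outside the imputed window.** An AEI with onset lag L (0 to 7 days) is counted only if 15 ≤ v + L ≤ 22, that is, 15 - L ≤ v ≤ 22 - L. For every L this gives exactly eight values of v, all inside the month, so the lag distribution does not matter:
- September, November: 1 - 8/30 = 73.3%
- October: 1 - 8/31 = 74.2%
- Mean of the three months: 73.6%

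**Sensitivity to the assumption on v**

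| Assumption | Share outside |
|---|---|
| Monday-Friday or Monday-Saturday vaccination, uniform or early-onset lags | 71-77% by month, mean about 74% |
| Linear weighting to start or end of month | 72.5-75.8% |
| All true days between 8 and 22 | 47% |
| All true days from 20 onward | 93-94% |

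For a single subject, with lags uniform over 0-7, the loss is 0% if the true day was the 15th, 50% if the 11th or 19th, and 100% for days 1-7 or 23 onward.

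**ISO week.** 15 September, 15 October and 15 November fall in weeks 37, 41 and 46. Each of these weeks holds seven days of its month, so the week is wrong in 1 - 7/30 = 76.7% or 1 - 7/31 = 77.4% of cases.

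**Effect on the overall rate.** If day-missing subjects have the same true AEI rate as others and all their AEIs carry a complete onset date, the relative fall is 0.736 × p. For a true rate of 5%:

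| p (assumed) | Relative fall | Estimated rate |
|---|---|---|
| 0.1% | 0.07% | 4.996% |
| 1% | 0.74% | 4.96% |
| 5% | 3.7% | 4.82% |
| 10% | 7.4% | 4.63% |

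For scale, Protocol Table 1 gives a 95% interval of 4.4-5.6% at 5,000 vaccinees and a 5% rate.

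**What reduces the fall**
- Background medically attended events at a steady rate are as likely to fall in one eight-day window as in another, so their net loss is about zero. If a share b of in-window AEIs is background, the fall is about 0.74p(1 - b); at b = 0.5 (assumed) and p = 10% this is 3.7%.
- An AEI with a missing onset day in the vaccination month is moved to the imputed 15th and counted. The reverse can also happen: a true vaccination on 28 October with onset recorded only as November becomes 15 October and 1 November, and is lost.

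**The case against.** The strongest reply is that nothing shows the rule will be used often. The documents give no share of day-missing records, the completeness table in 7.3.4 will disclose it, and at p = 1% the shift is far inside the confidence interval. This stands, and it sets the weight of the point.

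Four stronger readings are tempting, but the documents do not carry them.
- **That card AEIs are certainly lost.** The card asks only about the seven days after vaccination, and the SAP does not say that a card AEI is rejected when its date lies outside an imputed window. The onset-date rules in 12.2.1 suggest a date check but do not state one.
- **That 0.74p is the expected fall in every rate.** It is an upper bound given a uniform day, because background events and some AEIs without an onset day are still counted.
- **That the error differs by brand because missing days come from vaccinations given elsewhere.** The documents do not say where missing days arise. Patients vaccinated elsewhere are those who may not receive a card (SAP 3.3.2), and the primary denominator is limited to card recipients.
- **That the SAP contradicts itself by calling its imputation worst case.** That label covers AEI onset dates only.

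What remains is that, whenever the rule is used, it assigns a window and a week that the record does not support.

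**Conclusion.** The point holds as a minor defect in a derivation rule. For a day-missing subject, about 73-74% of true in-window AEIs with a complete onset date fall outside the imputed window, given a true day uniform over the month; the figure is an average. It applies to card-based and EHR-based rates if card AEIs are checked by date, and otherwise only to medically attended AEIs.

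On overall rates the relative fall is at most about 0.74p under the same assumption: negligible if p is 1% or less, and visible only if p reaches several per cent. A reader might infer that the study's rates are understated by three quarters, or by some known amount. The documents support neither, since p is not given. The misplacement into weeks 37, 41 and 46 does not depend on the uniformity assumption, though how often the week is wrong does.

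**What to change.** In SAP 12.2.1, state that vaccinations with a missing day are left out of both numerator and denominator of the weekly and cumulative 7-day incidence rates (7.3.2, 7.3.3, 7.3.6), and report the number left out by vaccine group.

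Do this at the level of the rates. Keep the subjects in the Cumulative vaccinated cohort, so that the completeness figure in 7.3.4 is not forced to 100%, and keep them in whole-season uptake (7.2), where the month is enough. Leave imputed dates out of the timeliness summary and the by-week uptake curve, or flag them there.

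The card does ask "What date were you vaccinated / was the vaccine given", but completing records from it should not be part of this change. It would be an added procedure at the practices, and the SAP's first version (11 December 2017) postdates the planned end of vaccination on 30 November.

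Cost: one rule and one reported count. The incidence denominator falls by the share p (5,000 becomes 4,950 at p = 1%), and the AEIs of the excluded subjects leave the rates, including those that would have been counted correctly. If no day is missing, nothing changes.

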12.2.4. Safety

Subjects who did not report an adverse event will be considered as subjects who did not experience adverse event.

For the analysis of fever/pyrexia, all subjects with a fever/pyrexia Read code recorded will be considered as having fever/pyrexia regardless of what temperature had been recorded. For the analysis of fever >38.5C and 39.5C, all subjects with a fever/pyrexia Read code recorded within 7-day post vaccination and with a recorded temperature above the specified thresholds (>38.5C and >39.5C) within 7-day post vaccination, independent of route of measurement, will be considered as having fever above the specified thresholds.

The following process steps will be followed for the cleaning of temperature values:

- Every value recorded has a field for units, which can be left blank. If the units specified “Fahrenheit” or “F”, the value will be converted to Celsius, using this formula: $(\text{Value} - 32) * 5/9$.
- Otherwise, if the value is between 90 and 110, the value will be converted from Fahrenheit to Celsius, using the above formula.
- Otherwise, if the value is between 3.3 and 4.1, it'll be assumed a decimal place error, and the value will be multiplied by 10.
- Otherwise, if the value is between 330 and 410, it'll be assumed a decimal place error, and the value will be divided by 10.
- Otherwise, if the value is between 3300 and 4100, it'll be assumed a decimal place error, and the value will be divided by 100.

All temperature values below 37.5 or above 41.5 will be discarded.

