14. ANNEX 3 ADVERSE DRUG REACTIONS SOLICITED IN THE CARD

Possible side effect or Condition in the 7 days after influenza vaccination	Start date of the symptom	Please tick as appropriate
Conjunctivitis – Sticky eyes	____/17	
Runny nose	____/17	
Blocked nose	____/17	
Epistaxis – Nose bleed	____/17	
Common cold	____/17	
Cough	____/17	
Sore throat	____/17	
Hoarse voice	____/17	
Wheezing	____/17	
Decreased appetite	____/17	
Nausea – feeling sick	____/17	
Vomiting – being sick	____/17	
Diarrhoea	____/17	
Fever (add temperature if measured)	____/17	
Allergic reaction (rash)	____/17	
Other allergic reactions	____/17	
Facial oedema (swelling)	____/17	
Local reaction to vaccine	____/17	
Rash	____/17	
Irritability	____/17	
Drowsiness	____/17	
Fatigue	____/17	
Tremor / shaking	____/17	
Seizure / fits	____/17	
Headache	____/17	
Muscle aches	____/17	
Joint pain	____/17	
Other		
1. _____	____/17	
2. _____	____/17	
3. _____	____/17	
Add below if more		

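### SAP 12.2.1 promises worst-case handling of missing AEI start dates but excludes AEIs with no onset month, which lowers card-based AEI rates wherever an undated tick reaches the extract

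*SAP*

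**What the plan says.** SAP 12.2.1 states its principle for AEI start dates that are incomplete or missing: "a conservative approach (worst case scenario) will be used for imputation for the vaccinated subjects". Two rules matter here.

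- Day missing, month known: "Month of onset = month of administration: day of administration will be used".
- Month not known: "Month or year missing: AEI not included in the statistical analysis".

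The card (Protocol Appendix 3, SAP Annex 3) has a tick box for each symptom and a separate column headed "Start date of the symptom", in which only the year is pre-printed. The symptom table is headed "Possible side effect or Condition in the 7 days after influenza vaccination", and section 4 of the card begins "Please report any side-effects/conditions in the 7 days after your flu vaccine". The written instruction there is "please tick the relevant box and indicate the severity"; it does not mention the date column.

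Under SAP 7.3.2 the primary denominator is every subject in the weekly or cumulative cohort who received a card. The numerator is those with an AEI on the card from day 0 to day 7. SAP 3.3.2 has practice staff enter card data into the EHR with a code that marks them as card-derived, and allows cards to come back up to day 14.

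**The concern.** The start date serves to place an AEI inside or outside the 7-day window. For a medically attended record it is the main evidence. For a card tick, the form has already asked about that window, so a blank date is weak evidence against eligibility. Excluding the AEI resolves the uncertainty toward no event, which is the reverse of worst case. Because patients are asked in words for a tick and a severity, but not for a date, undated ticks are foreseeable.

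The study is meant to detect a rise in reactogenicity quickly, so a downward bias is in the unhelpful direction. It would enter the primary card rates (SAP 7.3.2), the rates among card returners (7.3.6.2, which has no date rule of its own) and the card part of the secondary rates (7.3.3). The SAP text describes no count of AEIs excluded for a missing date and no analysis that includes them, so the loss would not be visible.

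**Working it through.** **1. The date rules side by side.** SAP 12.2.1 uses vaccination on 16 October 2017 as its example, so days 0 to 7 run from 16 to 23 October.

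| Onset held in the extract | SAP action | Counted? |
|---|---|---|
| October 2017, day unknown | set to 16 October (day 0) | yes |
| November 2017, day unknown | set to 1 November (day 16) | no |
| no month | AEI excluded | no |

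In the first row, 8 of October's 31 days lie in the window. The other 23 do not: 15 precede vaccination and 8 follow day 7. The AEI is counted anyway. In the third row a card tick comes with the form's own 7-day question and is discarded.

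**2. From exclusion to rate.** No rule removes a subject from the denominator because an AEI was excluded. The subject therefore remains as a non-event for that AEI through the numerator and denominator definitions.

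**3. Baseline from the plan.** Protocol Table 1, 10% coverage: n = 5,000, x = 50, p = 1.00%.

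- RSE = √((1 − p)/(np)) = √(0.99/50) = 14.1%.
- The Clopper-Pearson 95% CI is 0.74% to 1.32%.

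The table gives 14.1% and 0.7% to 1.3%, so the row is reproduced. It serves only as an illustration, since 5,000 is the number vaccinated, not the number given a card.

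**4. Effect on one AEI.** Let f be the share of that AEI's reporters whose tick for it reaches the extract with no onset month. Reported rate = p(1 − f). The documents give no f; the values below are assumptions.

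| f | Counted | Reported rate | Unclustered exact 95% CI |
|---|---|---|---|
| 0% | 50 | 1.00% | 0.74% to 1.32% |
| 10% | 45 | 0.90% | 0.66% to 1.20% |
| 20% | 40 | 0.80% | 0.57% to 1.09% |
| 30% | 35 | 0.70% | 0.49% to 0.97% |

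For a rarer AEI (0.1% in 1,000 vaccinees), the chance of seeing at least one is 1 − (1 − p)^n = 63.2%. With p replaced by p(1 − f) it becomes 59.4%, 55.1% and 50.4% for f = 10%, 20% and 30%.

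**5. Effect on any-AEI and category rates.** Here the factor is (1 − u), where u is the share of reporters left with no qualifying dated AEI at all, or none in that category. One dated tick keeps the subject in. u is not the same quantity as f and cannot be obtained from it without knowing how blanks cluster within a card.

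**6. What could be masked.** At f = 20%, a true 25% rise shows as 1.25 × 0.80 = 1.00 times the comparator. This holds only if the comparator, such as the clinical-trial rates named in the Protocol synopsis, does not carry the same loss.

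**The case against.** The strongest objection is that SAP 12.2.1 acts on dates extracted from the EHR, not on cards. Neither document says what date staff enter for an undated tick, or whether the field can be blank. If they enter the vaccination date, nothing is lost. If they enter the return or coding date, the exclusion rule is not triggered, but the event can fall after day 7 and be lost by another route. This stands: it makes the bias conditional, and any repair has to cover the second route too.

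Next, the form does ask for onset through its date column, and its wording on the window is mixed. The introductory text invites reports of any symptoms after the vaccination with no time limit, and the statement beside the no-event tick gives none either. This also stands. A tick indicates the window but does not prove it, and counting all undated ticks may admit some later events.

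Third, the rule is pre-specified, parallels the rule for vaccination dates, is reasonable for medically attended AEIs, and feeds analyses that SAP section 8 calls descriptive. The Protocol reports a card return rate of about 50% in the previous season, and non-returners already count as having no event, which may well matter more. That bears on priority; it does not reconcile the rule with its stated principle.

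A reader might infer more than the documents support:

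- That any patient with an undated tick counts as event-free. For any AEI this needs every other AEI to be undated or non-qualifying, and in the secondary analysis a dated medically attended record can still count.
- That SAP 12.2.4 makes this so: "Subjects who did not report an adverse event will be considered as subjects who did not experience adverse event". That sentence covers people who did not report, and an undated reporter did.
- That all card rates shrink by one common factor. Step 5 shows they do not.
- That the rule creates false differences by age, practice or week. This is possible if completeness varies, but nothing in the documents shows that it does.

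**Conclusion.** The concern holds in a limited form. For card-derived AEIs, excluding a record with no onset month contradicts the worst-case principle that SAP 12.2.1 sets for itself, and pushes the affected rates down. The bias is direct for the specific AEI. It reaches any-AEI and category rates only through subjects with no other qualifying dated AEI.

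The size cannot be stated. Under assumed undated shares of 10% to 30%, a true 1.00% becomes 0.90% to 0.70%. With complete dates, or with staff entering the vaccination date, the effect is nil. It should be fixed because the remedy is cheap and the direction is unhelpful. An unknown share and an undocumented transcription step do not support treating it as a flaw that invalidates the primary analysis.

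**What to change.** In SAP 12.2.1 add a rule for AEIs carrying the ADR-card code: where the onset month or the whole onset date is missing, set onset to the day of vaccination and count the AEI within 7 days. Keep the exclusion for medically attended AEIs.

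Confirm with the practices what date they record for an undated tick. Where the recorded date is only the card-return or coding date, treat onset as missing so that the same rule applies. The timeliness analysis in SAP 7.3.4 already needs both the onset date and the EHR entry date, so card records where the two coincide can be listed for this check. Coincidence is a flag, not proof.

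Report the number of AEIs imputed, show the cumulative rates with them excluded as a sensitivity row, and leave imputed onsets out of the timeliness summary.

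The cost is one derivation rule, one query to the practices and one table row. The SAP is dated 11 December 2017, after vaccination closed on 30 November, so the card can no longer change but the rule can. The downside is that some events after day 7 may be counted, because cards can come back up to day 14 and parts of the card give no window. The sensitivity row shows how much the choice matters.
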